5.3 Lifestyle restrictions

No restrictions are required.

5.4 Screen failures

Screen failures are defined as patients who signed the ICF to participate in the clinical study but are not subsequently entered in the Treatment Period. A minimal set of screen failure information is required to ensure transparent reporting of screen failure patients to meet the Consolidated Standards of Reporting Trials (CONSORT) publishing requirements and to respond to queries from regulatory authorities. Minimal information includes demography, screen failure details, eligibility criteria, and any SAE.

Patients who failed to meet 1 or more of the following eligibility criteria for participation in this study (screen failure) on initial evaluation may be rescreened once only, at the Investigator's discretion:

Inclusion criteria for rescreening

- Patients receiving or initiating HD or PD for treatment of ESRD for at least 12 weeks. Patients treated with HD must have access consisting of an AV fistula, AV graft, or tunneled (permanent) catheter. Patients on PD must have a functioning PD catheter in place.
- Patients (dialysis and non-dialysis, rHuEPO-users) must have a mean Hb level of ≥ 9 to ≤ 12 g/dL based on the mean of the 2 most recent central laboratory Hb values within 0.50 g/dL on 2 assays taken at least 7 days apart during the Screening Period. Non-dialysis rHuEPO-naïve patients must have a mean Hb level of ≥ 7 and ≤ 10 g/dL based on the mean of the 2 most recent central laboratory Hb values within 0.50 g/dL on 2 assays taken at least 7 days apart during the Screening Period.
- Hemodialysis patients should be on 3x/week dialysis with evidence of achievement of adequate dialysis as defined by $\text{stdKt/V} \geq 2.1$ in HD, and total (renal + PD) weekly $\text{Kt/V} \geq 1.7$ in PD documented twice during the 3 months preceding evaluation for the study.
- Negative swab test result to rule out active COVID-19 infection at the Screening Visit. If according to site procedures the test for COVID-19 infection cannot be performed at the first Screening Visit, the test should be performed as soon as possible thereafter but must be performed before the patient returns for the next study visit. Any participant who has had confirmed COVID-19 infection in the past, has fully recovered from symptoms at

least 14 days prior to Screening, and has a negative swab test result for COVID-19 infection at Screening may be included in the study.

Exclusion criteria for rescreening

- Systolic BP \geq 160 mmHg or diastolic BP \geq 95 mmHg (confirmed by repeated measurement), within 2 weeks prior to randomization.
- Any RBC transfusion during the Screening Period.
- Hospitalizations within the 12 weeks preceding study randomization for GI bleeding or CHF.
- Exposure to IV iron or use of TRIFERIC[®] in dialysate during the Screening Period (ie, 2 weeks before randomization [Day 1]).
- Exposure to iron-chelating agent (eg, deferoxamine/desferrioxamine, deferiprone or deferaxirox therapy) within the 6 weeks prior to the first Screening Visit.
- Gastroenteritis in the 4 weeks prior to randomization.

Rescreening is not allowed for any other criteria apart from those listed above.

Rescreened patients will be assigned a new patient number. An extra file will be included in the eCRF to record the original enrollment code (ECode). Rescreening will be documented so that its effect on study results, if any, can be assessed.

These patients should have the reason for study withdrawal recorded in the eCRF.

6 STUDY TREATMENTS

Study treatment is defined as any investigational product(s) (including marketed product comparator and placebo) or medical device(s) intended to be administered to a study participant according to the CSP. Study treatment in this study refers to roxadustat and rHuEPO.

6.1 Treatments administered

6.1.1 Investigational products

During the randomized Treatment Period, patients will be randomly assigned in 1:1 ratio to receive either roxadustat or rHuEPO for 2 weeks.

Patients will be provided roxadustat and rHuEPO and both treatments will be used according to their approved indication and dosage during the study. Refer to roxadustat and rHuEPO China Package Inserts for further details on these study treatments. For additional information regarding roxadustat, please refer to the IB.

6.1.2 Dose of study treatments

The starting dose of roxadustat will be calculated as per the China Package Insert. The recommended starting dose of roxadustat will depend on the body weight of the patient: 100 mg (45 to < 60 kg) or 120 mg (\geq 60 kg) in patients on dialysis (weight should be patient's empty weight prior to instillation of dialysate); 70 mg (40 to < 60 kg) or 100 mg (\geq 60 kg) in non-dialysis patients.

Roxadustat doses must be administered at least 2 days apart but no more than 4 days apart (eg, Monday, Wednesday, Friday). Dosing of roxadustat should be scheduled to occur on the day of Visit 4 (Day 15). Patients can take roxadustat at any time before or after dialysis treatment. On Day 1, roxadustat should be taken after the ferrokinetic study has completed. On Day 15 roxadustat should be taken at least 6 hours before the ferrokinetic study starts. The dose of roxadustat will not be adjusted during the study except for safety reasons as judged by the Investigator.

At Visit 2, all patients randomized to rHuEPO will receive a uniform brand of short-acting rHuEPO according to the dosage approved in the rHuEPO China Package Insert. Patients who were previously on rHuEPO (before Screening) will receive a uniform brand of short-acting rHuEPO based upon their previous dose of rHuEPO, and according to the dosage approved in the rHuEPO China Package Insert. For patients on a weekly dose of rHuEPO of 6000 IU, dosing will be BIW and for patients on a weekly dose of rHuEPO of > 6000 IU, dosing will be TIW. The rHuEPO can be administered either IV or SC depending on the route of administration used by the DD patients before the Treatment Period. The rHuEPO will be administered via the SC route for all patients who are NDD.

For patients who were rHuEPO-users before Screening, the initial dose selection of rHuEPO will be based on the patient's Hb levels, and average prescribed rHuEPO dose during the 4 weeks prior to the Screening Visit. For patients who are rHuEPO-naïve at study entry, the initial start dose of the study rHuEPO will be based on the patient's Hb levels and will be in accordance with the rHuEPO China Package Insert. Previously rHuEPO-naïve patients randomized to the rHuEPO arm may be trained by the site staff to self-administer SC injection on the day of randomization, if required. The rHuEPO may also be administered by a qualified person at the study site or at another hospital.

For patients who are already receiving the uniform brand of rHuEPO that will be used for the study, the initial rHuEPO dosing regimen in the study (starting from Visit 2) should be equivalent to their prior rHuEPO dosing regimen, unless a dose adjustment is needed per the Investigator's judgment.

For patients on any other short-acting rHuEPOs, a conversion ratio of 1:1 (equivalent dose) to the study rHuEPO should be used unless a dose adjustment is needed per the Investigator’s judgment.

For patients on long-acting rHuEPOs, the initial dose of the study rHuEPO will be determined using the conversion table (see [Table 3](#)), unless a dose adjustment is needed per the Investigator’s judgment.

The study rHuEPO dose can be adjusted on Day 8 during the 2-week Treatment Period, depending on the patient’s Hb levels. The rHuEPO dose may also be adjusted at any time during the Treatment Period by the Investigator for safety reasons, if judged necessary (see [Section 6.6](#) for details).

For patients already on rHuEPO, dosing of rHuEPO should be scheduled to occur on the day of Visit 2 (Day 1). Patients should be instructed not to take their rHuEPO dose in the morning before they attend for the randomization visit (Visit 2, Day 1). On Day 1, patients randomized to rHuEPO should have rHuEPO administered after the ferrokinetic study has completed. For patients randomized to rHuEPO, dosing of rHuEPO should be scheduled to occur on the day of Visit 4 (Day 15). On Day 15, patients randomized to rHuEPO should have rHuEPO administered within 1-2 hours before the ferrokinetic study starts.

Table 3 Initial dosing of rHuEPO for patients treated with an erythropoietic analogue at study entry

	Conversion ratio	Examples of converted initial epoetin alfa dose (IU/week) ^c
Darbepoetin alfa (µg/week) ^a	x 200	40 µg/week x 200 = 8,000 IU/week
Mircera [®] (µg/month) ^a	x 70 to 80 (Lower conversion ratio can be used for lower Mircera [®] dose) ^b	100 µg/month x 70 = 7,000 IU/week 200 µg/month x 80 = 16,000 IU/week

^a Mean weekly monthly dose prior to Screening Visit 1.

^b Per discretion of Investigator.

^c May be rounded if deemed necessary.

rHuEPO=recombinant human erythropoietin; IU=international unit.

Recombinant human erythropoietin must not be mixed with other drugs for injection.

If a patient misses a dose of study treatment (roxadustat or rHuEPO), the patient should make a note of this and inform the study site staff at their next study visit. They should continue with the next scheduled dose.

Details on dose modifications are in [Section 6.6](#).

6.1.3 Additional treatments

All patients will receive the same brand of liquid oral iron containing FeSO₄ to be administered as a single oral (liquid) dose of 12.5 mL (100 mg elemental iron) at Days 1 and 15 for the ferrokinetic study.

6.2 Preparation/handling/storage/accountability

Recombinant human erythropoietin can be administered either IV or SC. Administration of rHuEPO will be performed by the Investigator or a qualified member of the site staff in HD patients. In PD or NDD patients with CKD, rHuEPO can be self-administered SC by the patient or a caregiver after adequate training by site staff, unless the Investigator is of the opinion that the patient or caregiver is already adequately self-administering an rHuEPO analogue prior to the study. Previously rHuEPO-naïve patients randomized to the rHuEPO arm may be trained by the site staff to self-administer SC injection on the day of randomization. The rHuEPO may also be administered by a qualified person at the study site or at another hospital.

On Day 15, patients randomized to the roxadustat group should take the roxadustat in the morning, at least 6 hours before the ferrokinetic study starts. On Day 15, patients randomized to the rHuEPO group should take the rHuEPO within 1-2 hours before the ferrokinetic study starts. The time a patient takes the roxadustat and rHuEPO should be recorded in the eCRF.

Details on food restrictions on Days 1 and 15 are in Sections [4.1.1](#) and [8.1.1](#).

The Investigator or designee must confirm appropriate temperature conditions have been maintained during transit for all study treatment received and any discrepancies are reported and resolved before use of the study treatment.

Only patients enrolled in the study may receive study treatment and only authorized site staff may supply or administer study treatment. All study treatments must be stored in a secure, environmentally controlled, and monitored (manual or automated) area in accordance with the labelled storage conditions with access limited to the Investigator and authorized site staff.

The Investigator, institution, or the head of the medical institution (where applicable) is responsible for study treatment accountability, reconciliation, and record maintenance (ie, receipt, reconciliation, and final disposition records).

Further guidance and information for the final disposition of unused study treatment are provided in the Investigator Manual.

6.3 Measures to minimize bias: randomization and blinding

This is an open-label study in which a minimum of 20 patients and a maximum of 60 patients will be randomized in a 1:1 ratio to either roxadustat or rHuEPO. Results for Screening Period assessments for serum folate, vitamin B12, ALT, AST and TBL **must** be available before randomization. Randomization to treatment will be performed centrally using PAREXEL MATCH, an IVRS, in sequence and stratified by the following strata: NDD (rHuEPOuser, rHuEPO-naïve), DD-PD, and DD-HD patients.

The use of a central randomization will be implemented to avoid selection bias. Before the study is initiated, the telephone number and call-in directions for the IVRS will be provided to each study site.

If a patient withdraws from the study, then his/her enrollment/randomization ECode cannot be reused. Withdrawn patients will not be replaced.

Tables ran prior to database lock will be presented using a dummy treatment list to ensure decision bias is minimized.

6.4 Treatment adherence

Any change from the dosing schedule, dose interruptions, dose reductions, dose discontinuations should be recorded in eCRF.

The Investigational Product Storage Manager is responsible for managing the study treatment from receipt by the study site until the destruction or return of all unused study treatment. The Investigator(s) is responsible for ensuring that the patient has returned all unused study treatment. Patients who withdraw prior to the end of the Treatment Period due to a positive COVID-19 test result will be instructed to send any remaining study treatment to the study site by mail, when it is safe to do so.

6.5 Concomitant therapy

Concomitant medications are any prescription or over-the-counter preparations, including herbal products, TCM and “natural remedies”, used by a patient while participating in this clinical study. Any medication or vaccine including over-the-counter or prescription medicines, vitamins, and/or herbal products and “natural remedies” that the patient is receiving at the time of screening or receives during the study must be recorded along with:

- Reason for use
- Dates of administration including start and end dates
- Dosage information including dose and frequency

Patients should not take any new TCM and should not change the dose, schedule or brand of any TCM from beginning the of the Screening Period through the end of the Follow-up Period.

Patients taking oral iron before the study can continue taking this during the study. The dose of the oral iron should not be changed during the Treatment Period. The oral iron should not be taken in the morning on the day of ferrokinetic procedures and on this day, patients will be given a defined single dose of oral liquid elemental iron containing FeSO₄ used for the study.

For details of medications for which care should be taken when concomitantly administered with roxadustat or rHuEPO, refer to the respective China Package Inserts.

6.5.1 Prohibited medications/therapy

The following medications/therapies are prohibited during the study:

- Any other investigational drug: from randomization until EOS
- Any rHuEPO treatment during the Treatment Period, except for study treatment
- Iron-chelating agents (eg, deferoxamine/desferrioxamine, deferiprone or deferaxirox therapy): from 6 weeks prior to the first Screening Visit until the end of the Treatment Period
- Intravenous iron and TRIFERIC[®] in dialysate need to be stopped during the Screening Period (ie, 2 weeks before randomization [Day 1]), and should not be taken throughout the remaining Screening Period and the Treatment Period, but can be started again after the Treatment Period
- Any vitamin C formulation: from randomization until EOS.

For details of prohibited medications, refer to the respective China Package Inserts.

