- m Vital signs will include tympanic temperature, systolic and diastolic BP, pulse rate and respiratory rate. Blood pressure should be measured prior to the hemodialysis procedure. For patients on PD, BP should be measured in the morning prior to the patient performing the first exchange of the day. Pulse rate and BP should be measured in triplicate after being comfortably at rest in a seated position with the back and feet supported (ie, by chair back and floor or platform, respectively) quietly for at least 5 minutes.
- n Alanine aminotransferase, AST, ALP, albumin, and TBL.
- o Serum iron, ferritin, TIBC, TSAT, transferrin, soluble transferrin receptor. On Days 1 and 15, blood samples for these assessments will be collected **before** time T0 (ie, **before administration of the single dose of oral iron**). Note that serum iron and TIBC are included in the ferrokinetic study and should not be taken as part of the iron profile as well on Days 1 and 15. There is no need to collect duplicate sample for serum iron and TIBC. The sample collected before the single dose of oral iron is administered can serve for the iron profile as well.
- p Intravenous iron and TRIFERIC® in dialysate should be stopped at the Screening Visit (ie, at Visit 1) and should not be taken after stopping, throughout the Screening and Treatment Periods, but can be started again after the Treatment Period.
- q Must be conducted prior to randomization at Day 1 and prior to the hemodialysis procedures at Days 1 and 15.
- r The blood samples for the ferrokinetic study (serum iron and TIBC) must be taken immediately **before** the single dose of oral iron is administered (ie, immediately before time T0), and then at T1, T2 and T3 after the single dose of oral iron (sample for serum iron only). The window of allowance for the ferrokinetic study blood sampling will be ±3 minutes.
- s Collect from female patients of childbearing potential only.
- t Results for Screening Period assessments for **ALT, AST and TBL must be available before randomization**. Randomization must occur after the ferrokinetic study has completed, ie, after collection of the T3 serum iron sample. Patients will be randomly assigned in 1:1 ratio to either roxadustat or rHuEPO. Study treatment to be administered after randomization at Day 1.

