1.3 Schema

The general study design is summarized in [Figure 1](#).

Figure 1 Study design

The Screening Period will be approximately 2-3 weeks long, but may be greater or lesser, to ascertain the Hb eligibility criteria with up to 3 hemoglobin (Hb) tests. During the Screening Period, all patients who were on rHuEPO before entering the study will remain on the rHuEPO treatment they received. The rHuEPO dose may be adjusted for patients who were on rHuEPO before the Screening Period depending on the patient's Hb levels, at the discretion of the Investigator, in accordance with the rHuEPO China Package Insert.

The ferrokinetic study on Day 1 must be completed prior to randomization and prior to the hemodialysis procedure at Days 1 and 15. Patients will be randomly assigned in 1:1 ratio to either roxadustat or rHuEPO. Study treatment to be administered after randomization at Day 1.

*Ferrokinetic study at T0 (before single dose of oral iron [12.5 mL [100 mg elemental iron]]), and 1, 2 and 3 hours following the administration of a single dose of oral iron. The window of allowance for the ferrokinetic study blood sampling will be ± 3 minutes.

The blood samples for the ferrokinetic study (serum iron and TIBC) at the T0 timepoint must be taken immediately **before** the single dose of oral iron is administered.

On Days 1, 8, and 15 hemoglobin levels will be tested in the central laboratory for all patients. Additionally, for patients randomized to rHuEPO, Hb levels will be tested in the local laboratory on Days 1 and 8 for initial dose determination and dose adjustment. The rHuEPO dose may be adjusted on Day 8 of the Treatment Period, depending on the patient's Hb levels, for safety reasons, as determined by the Investigator, in accordance with the rHuEPO China Package Insert. On Day 15 (or at the discontinuation visit), Hb levels will be tested in the local laboratory for all patients who were on rHuEPO prior to the study, to decide what rHuEPO dose to restart patients on, or another appropriate course of treatment for anemia, after study treatment stops. For patients who were rHuEPO-naïve before entering the study, Hb levels may be tested in the local laboratory on Day 15 (or at the Discontinuation Visit) at the discretion of the Investigator, to determine an appropriate course of treatment for anemia in each patient.

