8.1.1 Primary efficacy assessments

The primary endpoint for this study is the GI iron absorption change from baseline (Day 1) to Day 15. At Days 1 and 15, serum iron level and TIBC will be determined immediately followed by administration of a defined single dose of oral liquid elemental iron containing FeSO₄ to all patients at time T0. Serum iron level at 1, 2, and 3 hours (each ± 3 minutes) following administration of the single oral iron dose (timepoints T1, T2, and T3) will then be determined. Gastrointestinal iron absorption will then be assessed by the total area under the curve (AUC) adjusted for serum iron level from sample obtained just prior to T0.

The primary endpoint is the relative difference in AUC for serum iron from baseline (Day 1) to Day 15 adjusted for study treatment and baseline hs-CRP level (\leq ULN, $>$ ULN). The model is described in Section 9.4.1.

The time the patient takes the single dose of oral iron and the collection time for each of the ferrokinetic study samples should be recorded in the eCRF.

On Day 1, after the ferrokinetic study has completed, the study treatment (roxadustat or rHuEPO) will be administered at the study site after randomization.

On Day 15, patients randomized to the roxadustat group should take the roxadustat in the morning, at least 6 hours before the ferrokinetic study. On Day 15 patients randomized to the rHuEPO group should take the rHuEPO within 1-2 hours before the ferrokinetic study. The time a patient takes the roxadustat and rHuEPO should be recorded in the eCRF.

All patients should not ingest any foods containing more than trace amounts of iron such as heme-rich foods, multivitamins with iron etc. for approximately 4 hours before and during the 3 hours of the ferrokinetic study. Patients are allowed limited small snacks with negligible amounts of iron during this 7-hour period. Patients may resume their normal dietary intake following collection of blood at the T3 time point. There is no restriction on drinking water, coffee or tea for the patient before the ferrokinetic study starts and during the ferrokinetic study.

Patients on HD will have their HD when the ferrokinetic study is completed (ie, after the T3 timepoint). For patients on PD, there are no timing restrictions for their PD in relation to the timing of the ferrokinetic study.

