9.4.1 Primary efficacy analyses

The primary efficacy endpoint is described in (Section 8.1.1). It is measured through change from baseline (Day 1) to Day 15 in log-transformed AUC of iron absorption from 0-3 hours based on the change in serum iron levels obtained just prior to T0 (time when single dose of oral iron is administered) and over a 3-hour period.

The AUC curve (for the calculation of the primary endpoint and associated secondary endpoints) will be determined for each patient at baseline (Day 1) and post-baseline, then the average of the changes from baseline (Day 1) will be evaluated for each treatment group. This is to be calculated for patient i as the sum of the area of each trapezium under the curve, adjusted for any iron present in sample obtained just prior to time T0. Let P_j be the serum iron level at timepoint T_j then the AUC for patient i at Visit X is

$$AUC_{X,i} = \sum_{j=0}^2 \left(\frac{P_{j+1} + P_j}{2} - P_0 \right)$$

Let d_i be the change from baseline for patient i and is defined as:

$$d_i = \log(AUC)_{Day\ 15,i} - \log(AUC)_{Baseline,i}$$

The difference in log (AUC) from baseline (Day 1) to Day 15 will be analyzed using an ANCOVA model, adjusting for study treatment and baseline hs-CRP level (\leq ULN, $>$ ULN).

If a patient withdraws before Day 15, their discontinuation visit will be used as the post-baseline primary measurement.

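### The vitamin C ban starts at randomisation, after the Day 1 iron test, so the baseline test falls outside it and the Day 15 test inside it

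*Protocol*

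**What the plan says.** Section 6.5.1 of the protocol lists vitamin C among the prohibited medications: "Any vitamin C formulation: from randomization until EOS".

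Footnote t of the Schedule of Activities fixes the order of events on Day 1: "Randomization must occur after the ferrokinetic study has completed, ie, after collection of the T3 serum iron sample". The schema (Section 1.3) agrees: "The ferrokinetic study on Day 1 must be completed prior to randomization". Section 4.1.1 gives the same sequence.

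The primary analysis (Section 9.4.1) uses both tests: "The difference in log (AUC) from baseline (Day 1) to Day 15 will be analyzed using an ANCOVA model". The same section says that AUC is computed for each patient at each visit and "then the average of the changes from baseline (Day 1) will be evaluated for each treatment group".

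The intake rule around both tests (Sections 4.1.1 and 8.1.1) is about iron only: "All patients should not ingest any foods containing more than trace amounts of iron such as heme-rich foods, multivitamins with iron etc".

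**The concern.** The ban begins between the two measurements that form the primary endpoint. Before Day 1, a patient who takes vitamin C is free to continue, including on the morning of the baseline test. By Day 15 the same patient must have stopped. If vitamin C affects the absorption of the 100 mg test dose of iron, the effect enters only the baseline half of the Day 15 minus Day 1 difference.

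This departs from how the protocol treats other agents that could disturb the test. In the same section, iron chelators are barred "from 6 weeks prior to the first Screening Visit until the end of the Treatment Period", and intravenous iron and TRIFERIC must stop about two weeks before Day 1. Section 6.5 keeps the dose of background oral iron constant over the Treatment Period and withholds it on test mornings. Each of these rules makes the two tests more alike, whereas the vitamin C rule makes them differ for any user.

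At stake are the interpretation of each arm's own change from baseline and, to a smaller extent, the variance of the primary endpoint when few patients are randomised.

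**Working it through.** **1. Is the gap real?** Day 1 runs in this order: T0 sample and oral iron, then T1, T2 and T3 samples, then randomisation, then first study dose. The ban starts at the randomisation step. Day 15 comes after it.

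| Agent or intake | Control starts | Day 1 test covered | Day 15 test covered |
|---|---|---|---|
| Iron chelators (6.5.1) | 6 weeks before first Screening Visit | yes | yes |
| IV iron, TRIFERIC (6.5.1) | Screening Period | yes | yes |
| Iron-containing food, multivitamins with iron (8.1.1) | about 4 hours before each test | yes | yes |
| Vitamin C (6.5.1) | randomisation | **no** | yes |

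Nothing else in the protocol closes the gap. No eligibility criterion in Sections 5.1 and 5.2 names vitamin C. Section 6.5.2 only discourages medication that is not listed. Section 6.5 requires vitamins to be recorded with dates and doses from screening, which identifies users but does not restrict them.

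**2. Effect on the endpoint.** Let a share *f* of patients use vitamin C at the Day 1 test only, and let it multiply their baseline AUC by *r*. Then, in each arm:

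- shift in mean log change = −*f* · ln *r*
- SD of change = √(*s*² + *f*(1 − *f*)(ln *r*)²), where *s* is the SD of change without vitamin C

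The shift is the same in both arms in expectation, so it cancels in the between-arm difference.

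**3. Inputs.** From the synopsis (Number of patients): a 2.7-fold effect, so δ = ln 2.7 = 0.993; SD 0.4 on the log scale; 8–10 patients per arm; two-sided 0.05; 90% power; two-sample t-test. The synopsis does not make clear whether 0.4 is the SD at one visit or the SD of the change, so both are carried:

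- single visit, visits uncorrelated: *s* = 0.4 × √2 = 0.566. This needs 8 per arm for 90% power, and 8 / 0.8 = 10 after 20% loss, which matches the stated 8–10.
- SD of change: *s* = 0.40. This needs 5 per arm, and 5 / 0.8 = 6.25, so 7 after loss.

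**Assumed, not in the documents:** *f* = 10% or 20%; *r* = 1.5 or 2.0.

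**4. Within-arm fold change.**

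- *f* = 0.2, *r* = 1.5: shift −0.2 × 0.405 = −0.081; 2.7 × e^(−0.081) = 2.49
- *f* = 0.2, *r* = 2.0: shift −0.2 × 0.693 = −0.139; 2.7 × e^(−0.139) = 2.35
- *f* = 0.1: shift −0.041 or −0.069, half as large

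**5. Power** (noncentral t, two-sided 0.05, δ = 0.993).

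| *s* | *f* | *r* | SD of change | 8 per arm | 10 per arm |
|---|---|---|---|---|---|
| 0.566 | 0 | – | 0.566 | 90.4% | 96.0% |
| 0.566 | 0.1 | 1.5 | 0.579 | 89.1% | 95.2% |
| 0.566 | 0.1 | 2.0 | 0.603 | 86.5% | 93.6% |
| 0.566 | 0.2 | 1.5 | 0.588 | 88.0% | 94.6% |
| 0.566 | 0.2 | 2.0 | 0.630 | 83.4% | 91.5% |
| 0.40 | 0 | – | 0.400 | 99.6% | 99.9% |
| 0.40 | 0.1 | 1.5 | 0.418 | 99.3% | 99.9% |
| 0.40 | 0.1 | 2.0 | 0.451 | 98.3% | 99.6% |
| 0.40 | 0.2 | 1.5 | 0.432 | 99.0% | 99.8% |
| 0.40 | 0.2 | 2.0 | 0.487 | 96.6% | 99.1% |

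At 30 per arm (the maximum of 60 randomised) power exceeds 99.9% in every row. Simulation of 200,000 trials per scenario at 8 and 10 per arm kept the mean between-arm difference at 0.99. It gave power of 88.2% and 83.5% for *f* = 0.2, *s* = 0.566, 8 per arm, against 88.0% and 83.4% above.

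**6. Chance imbalance.** If one arm of 10 happens to hold two more users than the other, the between-arm ratio moves by a factor *r*^0.2. That is 1.08 for *r* = 1.5 and 1.15 for *r* = 2.0.

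**The case against.** The strongest reply is that the primary inference is untouched. The hypothesis in Section 9.1.1 compares the arms, Day 1 use cannot depend on an arm not yet assigned, and any common shift cancels in expectation. On this view the sentence in Section 9.4.1 about averages per group is a step towards the comparison, since no within-arm test is planned. The first part stands in full. The second stands in part: no formal conclusion rests on an arm's own fold change, but it is a quantity the protocol says will be evaluated, and it is the scale on which the sample size assumption (2.7 times baseline) is expressed.

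Second, the protocol gives no reason for the ban, no effect size and no share of users, so every figure for the harm rests on assumption. This also stands. The gap itself does not depend on these figures.

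Third, the power loss is small. With 10 per arm analysed, the worst case shown is 91.5%, still above the 90% target. Power drops below 90% only at 8 per arm and only with an SD of change of 0.566. That is correct, but 8 per arm is what 10 per arm becomes after the 20% loss the synopsis allows for.

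Fourth, users can be identified from the medication record, and dietary vitamin C, coffee and tea are unrestricted at both tests anyway. An analysis can flag users, but it cannot recover a baseline taken under the Day 15 conditions. The dietary rules are at least the same on both days; the supplement rule is not.

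**Conclusion.** The concern holds as a minor design point worth correcting. On the protocol's own sequence the baseline test is always outside the vitamin C ban and the Day 15 test is always inside it, and no other rule closes the gap. The expected treatment difference is unbiased. The cost falls on the within-arm fold change (2.7 read as 2.49 to 2.35 with 20% users and a 1.5- to 2.0-fold effect) and on precision. The power loss at 8 per arm is up to 7 percentage points (90.4% to 83.4%) if 0.4 is a single-visit SD with uncorrelated visits, and 3 points (99.6% to 96.6%) if it is the SD of change. With few users, or near the maximum sample size, the effect is negligible. The timing gap is certain from the text; its size is not, because the user share and the effect on AUC are assumptions.

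**What to change.** In Section 6.5.1, start the vitamin C prohibition at the first Screening Visit, or at another lead time before the Day 1 ferrokinetic study chosen by the clinical team, and keep it at least through the Day 15 test. Both tests are then done under the same supplement rule, in line with how the section already handles chelators and intravenous iron.

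The cost is a one-line protocol change and an instruction to sites. Users go without vitamin C supplements for about 2–3 more weeks, the length of the Screening Period.
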